**Not determinable due to withdrawal during the ITI period**

A patient, who is withdrawn from the study treatment and discontinues the study before completion of the ITI period for any one of the reasons described in Section 7.3.3 of CSP, will have the ITI Outcome “Not determinable due to withdrawal during the ITI period”.

**6.1.5.4 Relapse**

Relapse in the tapering or follow-up period is defined as the occurrence of any of the following (with or without clinical symptoms) after complete ITI success:

1. Positive inhibitor ( $\geq 0.6$  BU/mL), on two consecutive assessments performed within 2-4 weeks  
 AND  
 2. An  $IR \leq 66\%$  of the expected IR, on two consecutive assessments performed within 2-4 weeks

For relapse the date at which relapse criteria was met will be recorded.

The time in days between relapse and ITI success will be derived, as the difference between the two dates.

**6.1.5.5 Bleeding**

All bleeding episodes will be recorded in the patient diary or in the CRF, including the following:

Swedish Orphan Biovitrum  
 Sobi.Elocta-003

Final 1.0  
 22/Oct/2020

TP-EP.BS-WW-001-05

Effective date: 29 Jul 15

Related to: SOP-EP.BS-WW-002

Page 24 of 64

**PAREXEL International**  
**Statistical Analysis Plan**

- Date/time of bleed
- Type of bleeding (spontaneous or traumatic)
- Whether bleeding was related to sports/physical activity
- Location of bleeding

**6.1.6 Safety Variables**

**6.1.6.1 Adverse Events**

In a clinical investigation, an adverse event (AE) is defined as any untoward medical occurrence in a patient administered a pharmaceutical product which does not necessarily have a causal relationship with this treatment. An AE can therefore be any unfavourable and unintended sign (including an abnormal laboratory finding, for example), symptom, or disease temporally associated with the use of a medicinal product, whether or not considered related to the medicinal product. Any progression/worsening of the underlying disease is also considered to be an AE. An AE is considered serious if it meets one or more of the following criteria:

- Results in death
- Is life-threatening (i.e., at immediate risk of death)
- Requires in-patient hospitalization or prolongation of existing hospitalization
- Results in persistent or significant disability/incapacity
- Is a congenital anomaly/birth defect (i.e., in an offspring to the study patient)
- Any other event that the investigator or company judges to be serious

Specifically, for this study, the following medically important events are also considered to be serious:

- Development of a confirmed positive inhibitor (>0.6 BU) during the tapering or follow-up periods
- A patient develops a Grade 2 or greater allergic reaction in association with administration of rFVIIIFc defined as follows using the Recommendations for Grading of Acute and Subacute Toxic Effects on the WHO scale
  - Grade 2: bronchospasm; no parenteral therapy needed
  - Grade 3: bronchospasm; parenteral therapy required
  - Grade 4: anaphylaxis

**PAREXEL International**  
**Statistical Analysis Plan**

- A patient develops a vascular thrombotic event, with the exception of IV injection site thrombophlebitis

In this patient population, bleeding episodes are not considered AEs, but if they meet a serious criterion they should be reported as a serious adverse event (SAE). Bleeding episodes that occur outside the clinic will be captured in the patient diary. Any relapse after successful ITI will also be captured as an SAE.

All AEs will be coded using MedDRA Version 22.0, including System Organ Class (SOC) and Preferred Term (PT).

A treatment-emergent adverse event (TEAE) is defined as an AE that begins or that worsens in severity after at least one dose of the study drug has been administered.

Any AEs with incomplete start and end dates/times will be treated as follows:

- Adverse events with unknown start and/or end times (but where the date is known) will be imputed with a time of 00:00 h for the tabulations but will be shown as NK:NK in the listings (where NK = Not Known).
- Adverse events with completely unknown start dates will be considered as treatment-emergent for the tabulations and will be shown as NK in the listings.

The following information will be recorded for AEs:

- Start and End Date
- Description of event (verbatim term)
- Status (stopped or not resolved)
- Severity (mild, moderate or severe)
- Relationship to study drug (related or not related according to investigator's judgement)
- What treatment was required (none, concomitant medication or other therapy)
- Whether it resulted in patient being terminated from the study
- Whether the AE was serious, and applicable seriousness criteria
- In case of death, whether autopsy was performed

## PAREXEL International

### Statistical Analysis Plan

The reporting period for AEs is described in Section 7.5.6.1.2 of the CSP. All SAEs experienced between informed consent and safety follow-up will be recorded, as well as any non-serious AEs between first dose of IMP and the safety follow-up visit.

#### **6.1.6.2 Clinical Laboratory Tests**

Blood samples will be collected according to the Schedule of Events (see Appendix 12.1) at screening, baseline visit and then every 12th week from start of the ITI treatment period until the end of tapering period. Blood and urine samples will also be collected at the end of treatment visit. The date of collection will be recorded in the CRF.

Hematology includes white blood cell count and differential, red blood cell, hemoglobin, hematocrit, and platelet count.

Blood chemistry includes sodium, potassium, chloride, total protein, total bilirubin, gamma glutamyl transferase, aspartate aminotransferase, alanine aminotransferase, alkaline phosphatase, blood urea nitrogen, serum creatinine, and glucose.

Urinalyses includes dipstick for blood, protein, and glucose. If the protein reading is positive ( $\geq 1+$ ), a full laboratory urinalysis, i.e. microscopic sediment evaluation will be required. Further investigation based on the dipstick and microscopic sediment results should be according to the investigator's discretion.

Samples will be analysed at a local laboratory.

Any clinically significant abnormal laboratory values will also be reported as AEs, and for those the following will be recorded in the CRF:

- Date of blood/urine collection
- Result of laboratory variable assessed
- Normal ranges at the local laboratory
- Adverse Event reference number

Laboratory values that are not both abnormal and clinically significant will not be recorded in the CRF.

#### **6.1.6.3 Vital Signs**

The following vital signs measurements will be obtained at each visit according to the Schedule of Events (see Appendix 12.1).

**PAREXEL International**  
**Statistical Analysis Plan**

- Systolic blood pressure (SBP) [mmHg]
- Diastolic blood pressure (DBP) [mmHg]
- Respiratory rate [breaths/minute]
- Pulse rate [beats per minute (bpm)]
- Body temperature (tympanic) [°C]
- Weight [kg]

Date and time of assessment will also be recorded. Clinical significant abnormal vital signs will be recorded as AEs.

#### **6.1.6.4 Physical Examination**

A general physical examination will be assessed and recorded according to the Schedule of Events (see Appendix 12.1). The body systems skin, lymph system, neck, chest/lungs, heart, vascular system, abdomen, musculoskeletal and neurological will be assessed as normal or abnormal. Abnormalities will be described. Any abnormalities reported at baseline will be recorded as medical history. New abnormalities or worsening of baseline abnormalities after the baseline visit will be recorded as adverse events.

#### **6.1.7 Pharmacokinetic Variables**

Unless otherwise stated, derivation of pharmacokinetic (PK) parameters will be the responsibility of Quantitative Clinical Development (QCD), PAREXEL International. Only PK parameters necessary for the evaluation of treatment success will be considered. The following PK parameters will be determined:

**Table 1      Pharmacokinetic Parameters after Repeated Dose Administration**

Parameter	Definition
$t_{1/2}$	Terminal Half-life (hours)
IR *#	Incremental recovery (IU/dL per IU/kg)

\*

\* Will be directly calculated and entered into the CRF by the investigator.

# Will be calculated and reported using data from both local and central laboratory

**PAREXEL International**  
**Statistical Analysis Plan**

**6.1.7.1 *Pharmacokinetic Parameter Calculation Methods***

PK parameters will be calculated by non-compartmental analysis methods from the activity-time data using WinNonlin (WNL) Professional (Version **6.3 or higher**) following these guidelines:

- Actual sampling times relative to dosing rather than nominal times will be used in the calculation of all derived PK parameters.
- There will be no imputation of missing data.
- All below the limit of quantification (BLQ) values pre-dose will be substituted by zeros. Terminal BLQ values will be disregarded.

The calculation of the PK parameters is described in Section 6.1.5.2.

**6.1.8 *Pharmacoeconomic Assessments***

Consumption will be assessed based on amount of administered drug as recorded in the CRF and in the diary.

Days missed from school or work will be recorded in the diary. The last day for consecutive span of missed days will be derived using start date and number of consecutive days after the first.

Hospitalizations will be recorded including start and end dates and will also be captured as SAEs. The number of days per hospitalization will be calculated as ‘end date’ – ‘start date’ + 1 (days).

**6.2 *Analysis Populations***

The final assignment of the patients to the different analysis populations will be made during the Data Review Meeting (DRM) before database lock and statistical analysis, based upon the criteria described in this section. In general, it is not planned to exclude any patient from any analysis set, as long as they reach each period respectively.

**6.2.1 *ITI Full Analysis Set***

The ITI full analysis set (ITIFAS) will include all patients receiving at least one dose of rFVIIIFc and will be used for describing efficacy and safety during ITI treatment.

**PAREXEL International**  
**Statistical Analysis Plan**

### **6.2.2 Tapering Period Full Analysis Set**

The tapering period full analysis set (TPFAS) will include all patients who achieve ITI Success and enter the tapering period of the study. All analyses describing efficacy and safety during this period will be based on this analysis set. In addition, some of the analyses (e.g. bleeding and hospitalization) combine the tapering period and the follow-up period (described in Section 6.2) into a longer, 48-week follow-up period. The TPFAS will be used for these analyses as well.

The tapering period is defined to start at the visit after confirmed ITI success.

### **6.2.3 Follow-up Full Analysis Set**

The follow-up full analysis set (FUFAS) will include all patients will include all patients who achieve ITI Success and enter the follow-up period in the study. Note that most analyses describing efficacy and safety during this period will be based on combined 48-week follow-up period mentioned in Section 6.2.2 instead. The FUFAS will be used for the generation of tables summarizing consumption.

The start of the follow-up period is defined as the day after the date of the last recorded visit in the tapering period.

## **6.3 Statistical Analysis Methods**

### **6.3.1 Listings and Descriptive Statistics**

All original and derived parameters as well as population characteristics will be listed. Relevant parameters will further be described using summary statistics.

Frequency counts (number of patients [n] and percentages) will be made for each qualitative variable. Missing values will be treated as a separate category.

Descriptive statistics (n, mean, standard deviation [SD], median, first and third quartile [Q1 and Q3], minimum and maximum) will be calculated for each quantitative variable (unless otherwise stated). The number of missing values will also be displayed.

All data that can be recorded in either the CRF or the patient diary (e.g. bleeding episodes) will be combined without regard to source in summary tables. In listings it will be indicated whether the entry is from the CRF or whether it is from the patient diary.

All listings will include repeated and unscheduled measurements.

**PAREXEL International**  
**Statistical Analysis Plan**

The following rules will apply to any repeated measurements:

- If the repeated measurement occurs prior to the first dose of study drug, then the last obtained value of any repeated measurement before first dose will be used in the descriptive statistics.
- If the repeated measurement occurs after the first dose of study drug, then the original value of any repeated measurements will be used in the descriptive statistics.

**6.3.1.1 *Definition of Visit for Summary Tables***

Two different definitions of visit will be used in the following sections.

- Nominal visit as recorded in the CRF:
  - Screening
  - Baseline
  - ITI Period, Week 2
  - Interim ITI Visit, Week 4 up to Week 60
  - ITI Assessment Visit 1 to 30
  - Tapering Period Visit Week 2 up to Week 16
  - Follow-up Visits Week 28 and Week 40
  - End of Treatment Visit
  - Final Safety Follow-up
- Time-based visit:
  - Visits for Screening and Baseline, visits in the tapering or follow-up period, the End of Treatment visit and the Final Safety Follow-up visit will be the same as for nominal visits
  - Visits in the ITI period, prior and including the visit where the first negative titer was measured will be mapped based on the nominal week number, for example "ITI Visit – Week 4" will be mapped to "ITI Period – Week 4"
  - Visits in the ITI Period will be mapped as follows:

## PAREXEL International

### Statistical Analysis Plan

- The Baseline and the Week 2 Visit will be retained as is
- All other scheduled visits will be mapped to the closest even number of weeks, i.e. if a Visit takes place on Day 79 (with Day 1 being the day of treatment start), then it will be mapped to “ITI Period – Week 12”. In general, the week will be determined by calculating 2 times the rounded integer result of (Visit Date – Treatment Start)/14. If two visits will be mapped to the same even number of weeks, only the first one will be used in summary statistics.
- No summary statistics will be shown for unscheduled and optional visits (i.e. visit in Week 20 of tapering period if period is prolonged). In listings unscheduled visits will be shown with period, study day and study week (defined as study day/7 rounded up).

If not explicitly stated otherwise, the term “visit” will refer to nominal visit. The mapping of visits that took place outside of the allowed window visit, defined in the CSP, will be discussed in the DRM.

#### **6.3.2 Rounding and Decimal Places**

The following rules will be followed with regard to the number of decimal places and presentation of data in the tables and listings of all data:

1. All data will be listed according to the number of decimal places presented in the source data.
2. Mean, median, Q1, Q3 and standard deviation will be tabulated to one more decimal place than the source data.
3. Minimum and maximum values will be tabulated to the same number of decimal places as the source data.
4. A maximum of three decimal places will apply to all summary statistics.
5. Percentages for frequencies will be displayed with 1 decimal place.
6. Percentage change of baseline will be displayed with 0 decimal places; for statistics of percentage change of baseline (e.g. mean and SD) the rules above apply.
7. Annualized event rates will be displayed with 1 decimal place; for statistics of annualized event rates the rules above apply.

**PAREXEL International**  
**Statistical Analysis Plan**

**6.3.3 Statistical Significance Level**

No formal statistical tests will be performed, and no confidence intervals will be presented. Therefore, it is not necessary to specify a significance level.

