#### Follow-up period

During the follow-up period patients will be treated prophylactically with dose and frequency prescribed by the investigator, according to the label and clinical response of the patient, for 32 weeks. Inhibitor titers and FVIII:C will be assessed locally at each visit. During the follow-up period the patient will be monitored for relapse. Any patients with relapse will conduct the end of treatment visit directly. After the patient has completed the end of treatment visit, they should be treated and followed-up according to investigator judgment and local practice and no further investigational medicinal product will be provided. A final safety follow-up call or visit will be conducted 1-2 weeks after the end of treatment visit.

Number of patients planned: 20 patients receiving at least one dose of rFVIIIFc

Diagnosis and main criteria for inclusion:	Male patients of any age diagnosed with severe haemophilia A Previously treated with any plasma-derived or recombinant conventional or extended half-life FVIII Diagnosed with high titer inhibitors (historical peak $\geq 5$ BU/mL according to medical records) Inhibitor titer $\geq 0.6$ BU at screening Documented failed previous ITI attempt(s)
Assessments:	Lab samples will be drawn for assessment of inhibitor titer and rFVIIIFc activity. Samples will be analyzed both locally and at a central laboratory. The results from the local laboratory will constitute the primary data of the study to be used for statistical analysis and clinical decision making. Occurrence of bleeds (spontaneous and traumatic) and associated details will be collected through a patient diary. Serious adverse events will be collected from informed consent until the safety follow-up visit. Adverse events will be collected from the baseline visit until the safety-follow-up visit. Clinical significant abnormal lab values as assessed by the investigator will be reported as AEs and the associated value (local laboratory) will also be collected. rFVIIIFc consumption, days missed from school or work and hospitalizations will be collected for health economic assessments.

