## 5.2 Study rationale

Current ITI regimens with conventional FVIII products usually require a long ITI treatment period with very high FVIII doses to achieve tolerance [15,17,33,34,35,36]. ITI success rates of 53-79% have been reported [15]. Patients who failed previous ITI attempts may be more difficult to tolerate with additional ITI attempts. There is therefore an unmet need to improve ITI treatment. As there is non-clinical evidence on immune modulatory effects of rFVIIIFc and spontaneously reported clinical ITI cases indicating potential benefits of rFVIIIFc in ITI as compared to conventional FVIII products, it is of interest to describe the outcome of ITI treatment performed with rFVIIIFc in patients who failed previous attempts.

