## **9 Statistical plan**

### **9.1 Determination of sample size**

Haemophilia A is a rare disease, hence there is a limited number of patients with severe haemophilia A who have developed inhibitors and have previously failed an ITI treatment attempt. Therefore no formal sample size calculation was performed. The 20 patients to be included is based on what is estimated to be needed to describe the outcome of ITI within a timeframe of 60 weeks as well as on what is also considered feasible to recruit.

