**PAREXEL International**  
**Statistical Analysis Plan**

**4. STATISTICAL BASIS FOR SAMPLE SIZE**

Haemophilia A is a rare disease, hence there is a limited number of patients with severe haemophilia A who have developed inhibitors and have previously failed an ITI treatment attempt. Therefore, no formal sample size calculation was performed. The 20 patients to be included is based on what is estimated to be needed to describe the outcome of ITI within a timeframe of 60 weeks as well as on what is also considered feasible to recruit.

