**6.3.12 Analysis Related to the Primary Objective**

**6.3.12.1 ITI Treatment Outcome**

The number and proportion of patients achieving each of the ITI success criteria, overall ITI success, partial success and treatment failure will be calculated and displayed in a summary table.

Partial success will also be further subdivided, depending on whether the second or the third criterion for success was achieved.

Treatment Failure will also be further subdivided by primary reason of failure, using the treatment failure criteria defined in Section 6.1.5.3.

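### The SAP rules out all confidence intervals, so the primary ITI success proportion in about 20 patients, and the relapse proportion in fewer, will carry no measure of precision

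*SAP*

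**What the plan says.** SAP 6.3.3 sets a rule for the whole analysis: "No formal statistical tests will be performed, and no confidence intervals will be presented". It then concludes: "Therefore, it is not necessary to specify a significance level".

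The primary analysis in SAP 6.3.12.1 consists of counts and percentages: "The number and proportion of patients achieving each of the ITI success criteria, overall ITI success, partial success and treatment failure will be calculated". The analysis set is the ITIFAS, meaning everyone who received a dose. Protocol 9.3.3 describes the same analysis. Relapse (SAP 6.3.13.2, Protocol 9.3.4.2) is a proportion in the TPFAS, which holds only patients who reached ITI success and entered tapering. No standard error or other precision measure is planned for either proportion.

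The planned size is "20 patients receiving at least one dose of rFVIIIFc" (Protocol synopsis). SAP section 4 says of it: "Therefore, no formal sample size calculation was performed". Protocol 9.1 gives the purpose: "The 20 patients to be included is based on what is estimated to be needed to describe the outcome of ITI", alongside feasibility of recruitment.

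The protocol is descriptive throughout. Its synopsis excludes inferential statistics and section 9.3.1 excludes hypothesis testing. It does not mention confidence intervals, so the explicit bar is found only in the SAP.

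**The concern.** SAP 6.3.3 treats intervals as if they were a by-product of testing. A test needs a null hypothesis and a significance level. An interval around a single proportion needs only a confidence level, and it says how closely the data fix the quantity being described. A study whose aim is to describe an outcome has as much use for that as a comparative one.

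The gap matters more here because the sample size was not chosen to meet any precision target. Nothing at the design stage tells a reader what 20 patients can resolve, so the study report is the only place left to say it. SAP 6.3.2 prints percentages to one decimal place, yet one patient in 20 moves the result by 1/20 = 5 percentage points. Relapse is more exposed still: a report of 0% relapse in a handful of patients invites a conclusion that the data cannot bear.

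**Working it through.** The documents give no precision figure, power or significance level, so there is no planned figure to reproduce. The check asks what interval would accompany the results that the plan could produce.

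**Inputs**
- n = 20 dosed patients (Protocol synopsis and 9.1; SAP section 4).
- Denominator for ITI success: the ITIFAS (SAP 6.3.12.1).
- Denominator for relapse: the TPFAS (SAP 6.2.2 and 6.3.13.2). Its size is unknown in advance; 4, 6 and 8 are used below as assumptions.
- Confidence level: 95%, two-sided. The documents give none, so this is an assumption.

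**Formula.** The exact (Clopper-Pearson) limits for x events in n patients are:
- lower = 2.5% quantile of Beta(x, n − x + 1);
- upper = 97.5% quantile of Beta(x + 1, n − x);
- for x = 0, lower = 0 and upper = 1 − 0.025^(1/n).

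**ITI success, n = 20**

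| Successes | Observed | Exact 95% interval | Width (points) | Wilson 95% interval |
|---|---|---|---|---|
| 5 | 25% | 8.7% to 49.1% | 40.4 | 11.2% to 46.9% |
| 7 | 35% | 15.4% to 59.2% | 43.8 | 18.1% to 56.7% |
| 10 | 50% | 27.2% to 72.8% | 45.6 | 29.9% to 70.1% |
| 15 | 75% | 50.9% to 91.3% | 40.4 | 53.1% to 88.8% |

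For any observed rate from 20% to 80% the exact interval is 38 to 46 points wide. The Wilson interval is somewhat narrower, at 33 to 40 points, so the message does not depend on the method.

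The normal approximation at 50% agrees: 1.96 × √(0.5 × 0.5 / 20) = 0.219, or about ±22 points. If only 16 patients were dosed (an assumption), 8/16 would give 24.7% to 75.3%.

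**Relapse**

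If 6 patients reach ITI success:
- 0/6: upper limit = 1 − 0.025^(1/6) = 1 − 0.541 = 0.459, so 0% to 45.9%.
- 1/6 (16.7%): 0.4% to 64.1%.

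With 0 relapses the upper limit is 60.2% if 4 patients succeed and 36.9% if 8 succeed.

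**The case against.** **The SAP follows the protocol.** The synopsis excludes inferential statistics, and many statisticians class confidence intervals as inferential. On that reading SAP 6.3.3 simply carries out the protocol. This has force: there is no contradiction between the documents, and a change to the SAP must be reconciled with the synopsis. It does not justify the rule itself, because the protocol never names intervals and one labelled descriptive leaves the no-test design intact.

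**Nothing is lost.** Counts, denominators and a listing of each patient's outcome will be reported, so a reader can compute the binomial interval. This is true, and it limits the point to presentation. Even so, a clinical reader should not have to calculate the precision of the primary result.

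**Comparison with published rates.** A reader might infer that the result is to be judged against earlier studies, since Protocol 5.2 says "ITI success rates of 53-79% have been reported" and Protocol 5.1.1 gives a range of 33% to 88%. The documents do not support that. Neither sets a benchmark or margin or plans a historical comparison; these figures are background and motivation. An interval would not make them a fair yardstick either. Protocol 5.1.1 says that success definitions and calculation methods differ between studies and that rescue ITI data are limited. Protocol 7.2.2 says that the International ITI study, the source cited for 53-79%, enrolled only patients at low risk of failure, whereas this trial enrols patients whose earlier ITI has failed.

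**Kaplan-Meier limits.** It is tempting to ask for pointwise limits on the time-to-success curves too. SAP 6.3.13.1 censors patients declared failures for lack of a titer decline, so the curve does not estimate the proportion who succeed. Limits around it would lend precision to the wrong quantity.

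**Conclusion.** The concern holds as a reporting weakness that should be corrected. The SAP's explicit rule leaves the primary proportion, and the relapse proportion, without any measure of precision, and lack of hypothesis testing does not require that rule. The unstated uncertainty is substantial: about 40 to 46 points of exact 95% interval width for 5 to 10 successes in 20, and an upper limit of 46% for relapse if none occurs among 6 successes.

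These sizes rest on 20 dosed patients, a two-sided 95% level and, for relapse, an assumed number of successes. The point does not show bias, a numerical error or a conflict between the documents, and it does not depend on any comparison with published rates.

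**What to change.** Replace the barring sentence in SAP 6.3.3 with wording such as:

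> *No hypothesis tests will be performed. Exact (Clopper-Pearson) two-sided 95% confidence intervals, for descriptive purposes only, will be given for the proportions with ITI success, partial success, treatment failure and relapse.*

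The statement that follows it, on the significance level, can then refer to tests alone. Add the interval columns to Table 14.2.1.1 (ITI outcome) and Table 14.2.1.7 (relapse). Add one line explaining that these intervals are descriptive and consistent with the protocol synopsis, which excludes inferential statistics. Leave the Kaplan-Meier tables without limits while declared failures are censored.

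The cost is one sentence, a few table columns and the one-line reconciliation. No new data, visits or patients are needed. If the database is already locked, the SAP's introductory section provides for additional analyses through an addendum. The intervals will be visibly wide, as they should be with this number of patients.
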